#### 4.0 Test Schedule

##### 4.1 Test Schedule: Phase I Dose Level 1 and Phase II (Phase I closed to accrual)

Tests and procedures	Baseline ≤14 days prior to Registratio	Active Monitoring								
		Initial Treatment or Retreatment 								
		Cycle 1	Cycle 2  & 3 			Cycle 4  & 5 		Cycles 6 – 18	Optional Pembro Year Day 1,	
		Day 1	Day 1	Day 2	Day 8	Day 15	Day 1	Day 2	Day 1	Day 1,
			±2 days*	±2 days	±2 days	±2 days	±2 days	±2 days	±2 days	±2 days
Physical exam and PS	X		X				X		X 	X 
Limited exam for AE assessment (as of Add 5) • Can be done with RN/APP					X	X				
Serum pregnancy test	X 									
HIV, hepatitis B and C, Quantiferon TB test	X									
Pembrolizumab administration R		X 	X				X		X	X
Cryoablation R				X 						
Leukapheresis and DC manufacturing R		X 								
Cellular Vaccine (DC) administration R				X 	X 	X 		X 		
Prevnar administration				X 				X 		
Chemistry Profile (Creatinine, T. Bili, AST, ALT, Alk Phos)	X	X	X				X		X	X
β2microglobulin (follicular only)	X									
Thyroid function cascade (TSH, reflex to T3, T4 if abnormal)	X		X				X		X	X
LDH	X						X 		X 	X 
Coagulation (INR)	X									
Hematology (ALC, WBC with differential, Hgb, PLT)	X	X 	X				X		X	X
Adverse Event Assessment	X		X	X	x	x	X	X	X	X

	Active Monitoring									
	Baseline	Initial Treatment or Retreatment 								
	≤14 days prior to Registratio	Cycle 1	Cycle 2  & 3 			Cycle 4  & 5 		Cycles 6 – 18	Optional Pembro Year Day 1,	
Day 1		Day 1	Day 2	Day 8	Day 15	Day 1	Day 2	Day 1		
Tests and procedures			±2 days*	±2 days	±2 days	±2 days	±2 days	±2 days	±2 days	±2 days
Radiologic evaluations (CT Chest, abdomen and pelvis, neck if clinically indicated, or PET/CT)	X 	X 					X 		X 	X 
Research blood for Immune Monitoring R		X 	X 				X 		X 	X 
Tumor biopsies 3,R		X 							X 	
FACT-Lym	X		X 				X 		X 	X 

**NOTE: All tests, and procedures and QOL indicated to be conducted on Day 1 of any cycle should be done PRIOR to treatment on that cycle**

**NOTE: For this study, 1 week is equal to 7 days and 1 month is equal to 28 days. Once cycle is equal to 3 weeks or 21 days**

**NOTE: If a patient goes off treatment for any reason prior to cycle 18, the patient will follow schedule 4.3 or 4.4 (see Section 13.0)**

**NOTE: Decision for optional additional year of Pembro is determined based on clinical response and approval by PI and sponsor.**

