  13. If an index tumor is amenable for excisional biopsy at Cycle 1 Day 1, then excisional biopsy may be performed at the discretion of the investigator. In this case, a separate index tumor will be identified for subsequent research biopsies.
  14. Cryoablation is performed on Day 2 of Cycle 2 only. If the previously identified tumor for cryoablation is decreased in size and can no longer be cryoablated, another tumor amenable to cryoablation will be identified for treatment. If no additional tumors can be identified for cryoablation, DC will be injected into the previously identified shrinking tumor.
  15. LDH performed on Day 1 of Cycles 4, 6, 8, 12, and 18.
  16. After Cycle 10, responsive or stable patients can be followed every other cycle by treating physician/provider until last cycle of treatment. However, patients will be followed by nurse at each cycle of treatment for adverse event assessment. They will be seen as needed by provider.
  17. If subject thyroid function tests are within normal at the end of treatment and have no clinical signs and symptoms of thyroiditis, thyroid function test does not need to be performed during active monitoring. If thyroid function tests are abnormal during treatment, these tests need to be followed until they return to normal.
  18. Retreatment starts at cycle 2.
  19. Every 3 months.
- R Research funded.

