  13. If an index tumor is amenable for excisional biopsy at Cycle 1 Day 1, then excisional biopsy may be performed at the discretion of the investigator. In this case, a separate index tumor will be identified for subsequent research biopsies.
  14. Cryoablation is performed on Day 8 of Cycle 2 only. If the previously identified tumor for cryoablation is decreased in size and can no longer be cryoablated, another tumor amenable to cryoablation will be identified for treatment. If no additional tumors can be identified for cryoablation, DC will be injected into the previously identified shrinking tumor.
  15. LDH performed on Day 1 of Cycles 4, 8, 12, and 18.
  16. After Cycle 10, responsive or stable patients can be followed every other cycle by treating physician/provider until last cycle of treatment. However, patients will be followed by nurse at each cycle of treatment for adverse event assessment. They will be seen as needed by provider.
  17. If subject thyroid function tests are within normal at the end of treatment and have no clinical signs and symptoms of thyroiditis, thyroid function test does not need to be performed during active monitoring. If thyroid function tests are abnormal during treatment, these tests need to be followed until they return to normal.
  18. Retreatment starts at cycle 2.
  19. Every 3 months.
- R Research funded.

**4.3 Test Schedule for Observation for patients who do not complete initial active treatment for any reason or do not have dendritic cells for retreatment.**

	Active Monitoring	
	Observation 	
	Day 1 of each observation cycle Every 3 months for 1 year (start at Week 62 or 8 weeks after last dose whichever is earlier)	Documented PD at any time during this protocol treatment or observation, prior to entering event monitoring, at End of Observation
Tests and procedures		
Physical exam and PS	X	X
Serum pregnancy test		
Pembrolizumab (MK-3475) administration R		
Cryoablation R		
Leukapheresis and DC manufacturing R		
Cellular Vaccine (DC) administration R		
Prevnar administration		
Chemistry Profile (Creatinine, TBili, AST, ALT, Alk Phos)	X	X
Thyroid function cascade	X 	
LDH	X	X
Coagulation (INR)		
Hematology (ALC, WBC with differential, Hgb, PLT)	X	X
Adverse Event Assessment	X	X
Radiologic evaluations (CT whole body, or PET/CT)	X	X
Research blood for Immune Monitoring R	X	X

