## 8.2 Treatment schedule modifications for pembrolizumab

Adverse events (both non-serious and serious) associated with pembrolizumab exposure may represent an immunologic etiology. These adverse events may occur shortly after the first dose or several months after the last dose of treatment. Pembrolizumab must be withheld for drug-related toxicities and severe or life-threatening AEs per Table 8.21 below. See Section 9.0 for supportive care guidelines, including use of corticosteroids.

**Table 8.21** Dose Modification Guidelines for Drug-Related Adverse Events for Pembrolizumab

CTCAE System/Organ/Class (SOC)	Adverse Event	Hold Treatment for Grade	Timing for Restarting Treatment	Treatment Discontinuation
Gastrointestinal disorders	Diarrhea or Colitis	2-3	AE resolves to Grade 0-1	AE does not resolve within 12 weeks of last dose or inability to reduce corticosteroid to 10 mg or less of prednisone or equivalent per day within 12 weeks
		4	Permanently discontinue	Permanently discontinue
Investigations	AST, or ALT, or Blood bilirubin	2	AE resolves to Grade 0-1	AE does not resolve within 12 weeks of last dose.
		3-4	Permanently discontinue (see exception below) a	Permanently discontinue
Metabolism and nutrition disorders	Glucose intolerance (Type 1 diabetes mellitus [if new onset]) or Hyperglycemia	T1DM or 3-4	Hold pembrolizumab for new onset Type 1 diabetes mellitus or Grade 3-4 hyperglycemia associated with evidence of beta cell failure	Resume pembrolizumab when patients are clinically and metabolically stable.
Endocrine disorders	Endocrine disorders – Other, specify: Hypophysitis	2-4	AE resolves to Grade 0-1. Therapy with pembrolizumab can be continued while endocrine replacement therapy is instituted	AE does not resolve within 12 weeks of last dose or inability to reduce corticosteroid to 10 mg or less of prednisone or equivalent per day within 12 weeks

CTCAE System/Organ/Class (SOC)	Adverse Event	Hold Treatment for Grade	Timing for Restarting Treatment	Treatment Discontinuation
Endocrine disorders	Hyperthyroidism	3	AE resolves to Grade 0-1	AE does not resolve within 12 weeks of last dose or inability to reduce corticosteroid to 10 mg or less of prednisone or equivalent per day within 12 weeks
		4	Permanently discontinue	Permanently discontinue

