  - For **Grade 3 or 4 diarrhea/colitis**, treat with intravenous steroids followed by high dose oral steroids.
  - When symptoms improve to Grade 1 or less, steroid taper should be started and continued over no less than 4 weeks.
- **Type 1 diabetes mellitus (if new onset, including diabetic ketoacidosis [DKA]) or  $\geq$ Grade 3 Hyperglycemia, if associated with ketosis (ketonuria) or metabolic acidosis (DKA)**
  - For **T1DM or Grade 3-4 Hyperglycemia**
    - Insulin replacement therapy is recommended for Type I diabetes mellitus and for Grade 3-4 hyperglycemia associated with metabolic acidosis or ketonuria.
    - Evaluate patients with serum glucose and a metabolic panel, urine ketones, glycosylated hemoglobin, and C-peptide.
- **Hypophysitis:**
  - For **Grade 2 events**, treat with corticosteroids. When symptoms improve to Grade 1 or less, steroid taper should be started and continued over no less than 4 weeks. Replacement of appropriate hormones may be required as the steroid dose is tapered.
  - For **Grade 3-4 events**, treat with an initial dose of IV corticosteroids followed by oral corticosteroids. When symptoms improve to Grade 1 or less, steroid taper should be started and continued over no less than 4 weeks. Replacement of appropriate hormones may be required as the steroid dose is tapered.
- **Hyperthyroidism or Hypothyroidism:**

Thyroid disorders can occur at any time during treatment. Monitor patients for changes in thyroid function (at the start of treatment, periodically during treatment, and as indicated based on clinical evaluation) and for clinical signs

and symptoms of thyroid disorders.

- **Grade 2** hyperthyroidism events (and **Grade 2-4** hypothyroidism):
  - In hyperthyroidism, non-selective beta-blockers (e.g. propranolol) are suggested as initial therapy.
  - In hypothyroidism, thyroid hormone replacement therapy, with levothyroxine or liothyronine, is indicated per standard of care.
- **Grade 3-4** hyperthyroidism
  - Treat with an initial dose of IV corticosteroid followed by oral corticosteroids. When symptoms improve to Grade 1 or less, steroid taper should be started and continued over no less than 4 weeks. Replacement of appropriate hormones may be required as the steroid dose is tapered.
- **Hepatic:**
  - For **Grade 2** events, monitor liver function tests more frequently until returned to baseline values (consider weekly).
    - Treat with IV or oral corticosteroids

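### Glucose is not scheduled at baseline, before any pembrolizumab dose or in observation, although Table 8.21 holds the drug for new-onset type 1 diabetes or Grade 3-4 hyperglycemia with beta cell failure

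*Combined protocol and SAP*

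**What the plan says.** Section 4.1 governs Phase II (Section 4.6). Its chemistry row reads "Chemistry Profile (Creatinine, T. Bili, AST, ALT, Alk Phos" and is marked at baseline, on Day 1 of every cycle and in the optional pembrolizumab year. Day 1 tests "should be done PRIOR to treatment on that cycle". The observation schedules in 4.3 and 4.5 carry the same panel: "Chemistry Profile (Creatinine, TBili, AST, ALT, Alk Phos". The dose level -1 schedule in 4.2 has it too, but is not in use. Schedule 4.4 has no laboratory tests.

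Table 8.21 instructs sites as follows: "Hold pembrolizumab for new onset Type 1 diabetes mellitus or Grade 3-4 hyperglycemia associated with evidence of beta cell failure". On the timing of immune-related events, Section 8.2 says: "These adverse events may occur shortly after the first dose or several months after the last dose of treatment".

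Glucose is called for in one place, Section 9.2, under the entry for type 1 diabetes or Grade 3-4 hyperglycemia: "Evaluate patients with serum glucose and a metabolic panel, urine ketones, glycosylated hemoglobin, and C-peptide".

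Section 15.17 lists type I diabetes as an uncommon known toxicity of pembrolizumab, at 0.1% to under 1%. Section 3.29c allows patients with stable diabetes to enroll.

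**The concern.** Hyperglycemia is a laboratory finding and cannot be graded without a glucose value. The plan attaches a dosing action to a grade of it, yet a site that follows the schedule exactly never measures glucose routinely. The Section 9.2 measurement comes after someone already suspects the event.

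Three things are at stake:

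- **Patient safety.** Asymptomatic hyperglycemia could go unrecognized while further 3-weekly doses are given, or during observation, when Section 8.2 says such events can still begin.
- **Safety data.** Safety is a Phase II secondary goal (2.223). Section 10.622 requires Grade 3 and 4 events to be submitted whatever their attribution, and 16.325 tabulates maximum grades. An abnormality that is not measured cannot enter those tables.
- **Interpretation.** A patient admitted with stable diabetes has no baseline study glucose against which to read a later value.

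**Working it through.** **Search for a scheduled glucose.** The plan states no figure on this point, so the first step is a document check.

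| Place | Glucose, HbA1c, metabolic panel or urinalysis? |
|---|---|
| 4.1, 4.2, 4.3, 4.5 chemistry rows | No; five named analytes |
| Footnotes to those schedules | No |
| 4.4 event monitoring | No laboratory tests |
| 3.17 eligibility laboratory values | No |
| 10.61 solicited adverse events | Hyperglycemia not listed |
| 9.2 supportive care | Yes, as work-up of the event |

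Scheduled glucose time points: 0. By contrast, thyroid function, also tied to Table 8.21 entries, has its own row at baseline and on Day 1 from Cycle 2.

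**How many draws could carry it.** Under 4.1: 1 baseline + 18 initial cycles + up to 18 optional cycles (Section 13.2) = 37. Footnote 18 says "Retreatment starts at cycle 2", so a full retreatment course (Cycles 2 to 18) adds up to 17. These are maxima: the optional year needs approval, and patients in complete response may stop early.

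**How many patients.** Phase II uses dose level 1 (7.5), so dose level 1 is the MTD and Phase I contributes at most 6 evaluable patients. From 16.12, the evaluable maximum is 6 + 28 = 34 and the accrued maximum is 6 + 1 + 31 = 38. Section 16.31 gives 28 in total.

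**Chance that at least one case of type 1 diabetes occurs.** This assumes that the 15.17 rate applies to the combination and that patients are independent: P = 1 − (1 − p)^n. Since 1% is an exclusive upper bound, the right-hand column is a limit that is not reached.

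| n | p = 0.001 | p = 0.01 |
|---|---|---|
| 28 | 1 − 0.999^28 = 0.028 | 1 − 0.99^28 = 0.245 |
| 34 | 1 − 0.999^34 = 0.033 | 1 − 0.99^34 = 0.289 |
| 38 | 1 − 0.999^38 = 0.037 | 1 − 0.99^38 = 0.317 |

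Expected cases at n = 34: 34 × 0.001 = 0.034 to just under 34 × 0.01 = 0.34.

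These figures give the chance that a case occurs. They do not give the chance that one is detected late or missed, and nothing in the documents allows that to be estimated.

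**The case against.** The strongest reply is that the hold rule does not depend on a routine glucose. It requires new-onset type 1 diabetes, or Grade 3-4 hyperglycemia together with evidence of beta cell failure, so an isolated raised glucose would not by itself decide a hold. Clinically evident cases have several routes to detection. Adverse events are assessed at each cycle from Cycle 2, and on Days 1, 2, 8 and 15 of Cycles 2 and 3. When provider visits are reduced after Cycle 10, "patients will be followed by nurse at each cycle of treatment for adverse event assessment". Observation visits include an examination and adverse event assessment. Patients are told to report any side effect (15.191), and the endocrine nursing item (15.196) provides for laboratory tests on a physician's order. All of this stands, and it confines the gap to asymptomatic or unrecognized hyperglycemia. Item 15.196 names four endocrine conditions as examples, none of them diabetes, so the symptom route is general.

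A second reply is that the panel fits a choice by frequency. The ALT, AST, alkaline phosphatase, creatinine and thyroid abnormalities it covers are in the common tier of 15.17, while type I diabetes is in the uncommon tier. Hypophysitis, also uncommon and with its own hold, has no dedicated test either. This is a fair reading, but the plan does not give that reason, and glucose could be added to a draw already being made.

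Third, the reporting consequence is limited. Under 10.62, Grade 1 hyperglycemia need not be submitted, and Grade 2 only if related. That is correct. Under-ascertainment matters for Grade 3-4 events and related Grade 2 events. Similarly, 3.29c already requires a judgment that diabetes is stable at entry, so what is missing at baseline is a study value, not all assessment.

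**Conclusion.** The concern holds. Glucose is scheduled at none of the time points in the operative schedules, while a graded glucose abnormality forms part of a pembrolizumab hold criterion. The consequence is possible late detection of asymptomatic hyperglycemia and incomplete safety tables. The hold rule itself is sound.

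The likely number of type 1 diabetes cases is small: fewer than 0.34 expected among 34 patients, if the monotherapy listing in 15.17 carries over to this combination. The number that would be found late is unknown. Sites may measure glucose in ordinary care, but the documents do not require it. The primary endpoint, type I error, power and decision rule are untouched. The change is recommended because it is cheap and concerns a listed, potentially serious toxicity; the trial's efficacy conclusion does not depend on it.

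**What to change.** Add glucose to the analytes named in the chemistry row of Sections 4.1, 4.3 and 4.5, at every visit where the panel is already drawn, including baseline. State that a Grade 3-4 value prompts the existing Section 9.2 work-up (metabolic panel, urine ketones, HbA1c and C-peptide), and that the result of the work-up decides whether pembrolizumab is held. Leave the Table 8.21 criterion as it is.

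The cost is one analyte per existing blood draw, with no new visit or procedure. The downside is that some incidental hyperglycemia of non-immune origin will need evaluation, for example in patients with known diabetes.

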**\*Cycle 2 Day 1 window ±4 days**

1. For women of childbearing potential only. Must be done ≤7 days prior to registration. Pregnancy testing will be repeated if patient qualifies for re-treatment.
2. If the previously cryoablated lesion no longer appears viable by imaging, DC will be injected into the previously treated region. Pevnar will be injected in the region of the first treated lesion. Patient will get DC until supply exhausted or maximum of 8 doses whichever comes first.
3. An index tumor for biopsy is identified as accessible via needle biopsy that is not the cryoablation site.
4. An index tumor lesion that is not the cryoablated or treated lesion may be biopsied if it is easily accessible or amenable to image-guided biopsy; Day 1 Cycle 1 (may be done any time prior to Day 1 Cycle 1), Day 1 Cycle 6, and Day 1 Cycle 19 (8 weeks post last dose of treatment) and at the time of disease progression. For the time point of Day 1 Cycle 1 and at time of disease progression, if excisional biopsy is done for diagnostic purposes, then remaining tissue after pathology review can be used for research studies.
5. Up to 28 days prior to registration.
6. Blood draw for immune monitoring and FACT-Lym should be collected prior to pembrolizumab administration, DC vaccine injection and Pevnar administration. Blood draw for immune monitoring and FACT-Lym during treatment period will be collected on Day 1 of Cycles 1,

- 2, 4, 6, 8, 12 and 18.
  7. Cycle 1 Day 1 order: blood for immune monitoring, leukapheresis, and pembrolizumab administration.
  8. CT or MRI does not need to be repeated if the baseline CT whole body or PET/CT is deemed adequate by study investigator.
  9. Imaging performed during active treatment period on Day 1 of Cycles 4, 8, 12, and 18. All patients who received at least 2 cycles of treatments and do not have evidence of PD should be evaluated for formal clinical response.
  10. If not enough DC, then proceed to Cycle 6.
  11. Patients with residual or progressive disease may be retreated if deemed clinically feasible. See Section 7.12. These patients will follow the same test schedule for retreatment, starting with Day 1 Cycle 2.
  12. If the baseline CBC with differential is more than 3 days from the date of leukapheresis, then a CBC with differential needs to be drawn at or within 3 days from leukapheresis.
  13. If an index tumor is amenable for excisional biopsy at Cycle 1 Day 1, then excisional biopsy may be performed at the discretion of the investigator. In this case, a separate index tumor will be identified for subsequent research biopsies.
  14. Cryoablation is performed on Day 2 of Cycle 2 only. If the previously identified tumor for cryoablation is decreased in size and can no longer be cryoablated, another tumor amenable to cryoablation will be identified for treatment. If no additional tumors can be identified for cryoablation, DC will be injected into the previously identified shrinking tumor.
  15. LDH performed on Day 1 of Cycles 4, 6, 8, 12, and 18.
  16. After Cycle 10, responsive or stable patients can be followed every other cycle by treating physician/provider until last cycle of treatment. However, patients will be followed by nurse at each cycle of treatment for adverse event assessment. They will be seen as needed by provider.
  17. If subject thyroid function tests are within normal at the end of treatment and have no clinical signs and symptoms of thyroiditis, thyroid function test does not need to be performed during active monitoring. If thyroid function tests are abnormal during treatment, these tests need to be followed until they return to normal.
  18. Retreatment starts at cycle 2.
  19. Every 3 months.
- R Research funded.

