### 3.0 Patient Eligibility

#### 3.1 Inclusion Criteria

- 3.11 Age  $\geq 18$  years.
- 3.12 Histological confirmation of biopsy-proven non-Hodgkin lymphoma, *excluding* chronic lymphocytic leukemia, primary CNS lymphoma and Burkitt's lymphoma.  
Note: Small lymphocytic lymphoma (SLL) is allowed.
- 3.13 Patients with indolent NHL must have had  $\geq 1$  regimen of rituximab-containing regimen.  
Note: This includes FL, marginal lymphoma and MALT.
- 3.14 Patients with aggressive NHL must have had  $\geq 2$  regimens.  
Note: This includes DLBCL, MCL, PMBCL, and T cell lymphoma.
- Patients with aggressive NHL must have received prior therapy – at a minimum:
- Anti-CD20 monoclonal antibody unless tumor is CD20 negative and
  - An anthracycline containing regimen.
  - Transformed FL must have had therapy for FL and be refractory to chemotherapy for DLBCL.
- Chemotherapy refractory disease in aggressive NHL is defined as
- Stable disease of  $\leq 12$  months or progressive disease as best response to most recent chemotherapy containing regimen.
  - Disease progression or recurrence  $\leq 12$  months of prior autologous SCT.
- Patients with aggressive NHL must have failed autologous HSCT, or are ineligible or not consenting to autologous HSCT.
- 3.15 Patient must have at least 3 measurable lesions that are  $\geq 1.5$  cm in one dimension. One of the lesions must be  $\geq 2.0$  cm and is amenable to image-guided cryoablation and multiple vaccine injections as determined by Interventional Radiology and PI (including tumors that can be safely accessed using imaging guidance and treated with minimal risk to adjacent structures).
- 3.16 ECOG Performance Status (PS) 0 or 1 (Appendix I).
- 3.17 The following laboratory values obtained  $\leq 14$  days prior to registration.
- Absolute neutrophil count (ANC)  $\geq 1000/\text{mm}^3$
  - Absolute lymphocyte count  $\geq 200/\text{mm}^3$
  - Platelet count  $\geq 50,000/\text{mm}^3$
  - Hemoglobin  $\geq 8.0$  g/dL
  - Total bilirubin  $\leq 1.5$  x upper limit of normal (ULN), unless due to Gilbert's disease.
  - Aspartate transaminase (AST/SGOT) and alanine transaminase (ALT/SGPT)  $\leq 2.5$  x ULN
  - Creatinine  $\leq 1.5$  x ULN or calculated creatinine clearance  $\geq 60$  mL/min for subject with creatinine  $> 1.5$  x institutional ULN
- 3.18 Negative serum pregnancy test for women of childbearing potential  $\leq 7$  days prior to registration.  

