### 7.112 Phase I dose level 1 schedule Treatment by Cycle

Cycle	Duration	Timepoint	Day
Cycle 1	3 weeks	Week 1 to Week 3	Day 1: Leukapheresis followed by pembrolizumab (DC manufacturing in lab)
Cycle 2	3 weeks	Week 4 to Week 6	Day 1: Pembrolizumab Day 2: Cryoablation  of tumor followed by intra-tumor injection of DC and injection of Prevnar13 in nearby region Day 8: DC as per section 7.115  Day 15: DC as per section 7.115 
Cycle 3	3 weeks	Week 7 to Week 9	Day 1: Pembrolizumab Day 2: Prevnar13, DC per Section 7.115  Day 8: DC per Section 7.115  Day 15: DC per Section 7.115 

Cycle	Duration	Timepoint	Day
Cycles 4 - 5	3 weeks		Day 1: Pembrolizumab Day 2: Prevnar13, DC as per Section 7.3 
Cycles 6 - 18	3 weeks		Day 1: Pembrolizumab Tumor biopsy on Day 1 of Cycle 6 only

1. If supply exhausted, start Cycle 6 of pembrolizumab.
2. If the previously identified tumor for cryoablation is decreased in size and can no longer be cryoablated, another tumor amenable to cryoablation will be identified for treatment. If no additional tumors can be identified for cryoablation, DC will be injected into the previously identified shrinking tumor.

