## 11.0 Treatment Evaluation

**NOTE:** For assessment of index (target) and non-target lesions on whole body scan performed after completion of DC treatment, the baseline whole body scan will be used to assess overall treatment response of index (target) and non-target lesions. Include up to 6 index (target) lesions as measurable disease when assessing overall clinical response. The treatment lesion(s) is the lesion(s) that is cryoablated. This treatment lesion will be measured only at baseline and will not be included in assessment of overall clinical response, and will not be followed or measured.

**NOTE:** Subject(s) with progressive disease on anti-PD-1 monoclonal antibody alone prior to receiving cryoablation and intra-tumor injection of autologous DC will be continued on treatment to assess clinical response with the addition of these therapy as long as the provider and the investigator deemed clinically safe and reasonable.

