## 16.4 Analysis of other endpoint

### 16.41 Definitions and Analyses of Radiologic Endpoints

Measurements of index lesion(s) (non-cryoablated lesion) will be evaluated over time for each patient as a marker of systemic immune and treatment response to Pembrolizumab and localized treatment with cryoablation and DC. The index lesion(s) will be selected by the treating physician/investigator and are non-cryoablated node. The percent change from baseline in index lesion measurements will be assessed over time. Differences in values over time will be summarized descriptively and graphically. In addition, patients will be classified into one of the following categories based on the best response seen in the index lesion(s):

- Complete response: disappearance of the node
- Partial response:  $\geq 50\%$  of decrease in measured dimension
- Stable: between  $50\%$  decrease to  $\leq 25\%$  increase in dimension
- Progression:  $>25\%$  increase in measured dimension

While the evaluation of index lesion(s) may be part of the assessment of overall response, it is not the sole criteria for time to progression. The whole body CT or PET/CT will be used to assess overall clinical response and time to progression using the standard Cheson criteria, as detailed in Section 11.

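### The cryoablation lesion can be replaced because it shrank on pembrolizumab, and only the lesion actually ablated is excluded, so early response can decide which lesions count toward ORR

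*Combined protocol and SAP*

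**What the plan says.** For dose level 1 and Phase II, leukapheresis and the first pembrolizumab dose fall on Cycle 1 Day 1 ("Day 1: Leukapheresis followed by pembrolizumab", Section 7.112). The second dose is on Cycle 2 Day 1, and ablation follows a day later: "Cryoablation is performed on Day 2 of Cycle 2 only" (4.1, footnote 14).

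The same footnote says that, if the planned tumor has shrunk and cannot be ablated, "another tumor amenable to cryoablation will be identified for treatment". If no other tumor can be ablated, the dendritic cells (DC) go into the shrinking one. Footnote 2 of 7.112 repeats the rule, and the dose level -1 schedule has its own version.

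On response, Section 11.0 says: "The treatment lesion(s) is the lesion(s) that is cryoablated". That lesion "will not be included in assessment of overall clinical response, and will not be followed or measured". Up to six index lesions are scored against the baseline scan. Section 16.41 adds: "The index lesion(s) will be selected by the treating physician/investigator and are non-cryoablated node". Section 3.15 sets the entry minimum: "Patient must have at least 3 measurable lesions".

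No section fixes the index list before the first pembrolizumab dose, says how a swapped-out lesion is scored, or plans an analysis of swapped patients.

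**The concern.** The trigger for the swap is a post-baseline outcome, namely shrinkage on pembrolizumab. The exclusion in 11.0 attaches to the lesion actually ablated, not to the one planned. A swap therefore takes a lesion that is still ablatable out of the assessment, and nothing keeps the shrunken lesion from being chosen as an index lesion. Both effects tend to make the measured fall larger.

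PR on CT needs a fall of at least 50% in the sum of products of diameters (SPD). Under the three-lesion minimum only two lesions remain in the sum after one is ablated, so one exchange can change the category. The primary decision in this open-label, single-arm trial counts those categories against a fixed cut-off.

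A related gap is that a tumor injected with DC but not ablated is not a treatment lesion under the 11.0 definition, so it stays countable although it was treated locally.

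**Working it through.** **The plan's own figures.** Sections 16.312 and 16.314 give n = 28, success at 13 or more responders, null ORR 30% and alternative 53%. With exact binomial tails:
- P(X ≥ 13 | 28, 0.53) = 0.812; the plan states 81%.
- P(X ≥ 13 | 28, 0.30) = 0.0491; the plan states 0.05.

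The design reproduces.

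**Can a swap change the category on CT criteria?** The change is (follow-up SPD ÷ baseline SPD) - 1. Sizes are assumed. A is the planned lesion, B the substitute and C another index lesion.

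*Removing the substitute is enough.* Let B and C each be 4.0 cm² at baseline, B unchanged and C falling to 1.8 cm² (-55%).
- A ablated as planned, so B + C count: 8.0 to 5.8 = -27.5%, stable disease.
- B ablated and A not added, so C alone counts: 4.0 to 1.8 = -55%, PR.

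*With the planned lesion also entering.* A is 2.0 × 2.0 falling to 0.9 × 0.9 cm, B stays at 2.0 × 2.0 and C at 1.5 × 1.5.
- B + C: 6.25 to 6.25 = 0%, stable disease.
- A + B + C: 10.25 to 0.81 + 4.00 + 2.25 = 7.06, or -31%, stable disease.
- A + C: 6.25 to 0.81 + 2.25 = 3.06, or -51%, PR.

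This second example sits close to the threshold. If A shrinks only to 1.0 × 1.0, A + C goes from 6.25 to 3.25, which is -48%.

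*Dilution.* With m equal lesions in the sum, exchanging a lesion at 0% for one at -75% moves the total by 75/m points: 37.5 for m = 2, 25 for m = 3 and 12.5 for m = 6.

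**Effect on the decision rule.** The number of conversions is an assumption. If k true non-responders are scored as PR at a true ORR of 30%, the false-positive rate is P(X + k ≥ 13), with X binomial (28, 0.30):
- k = 0: P(X ≥ 13) = 4.9%
- k = 1: P(X ≥ 12) = 10.3%
- k = 2: P(X ≥ 11) = 19.1%

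**Direction.** An illustrative simulation assumed:
- 3, 5 or 7 lesions of 1.5 to 4.0 cm, the planned one at least 2.0 cm;
- between-lesion correlation of 0.3, 0.6 or 0.9;
- 60% of the eventual log change in area present at Cycle 2;
- a swap when the planned lesion is below 2.0 cm and more than 10% smaller in diameter, to the largest other lesion if that is at least 2.0 cm;
- every non-ablated lesion counted.

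With true ORR set to 30%, swaps occurred in 15% to 33% of patients and apparent ORR was 31% to 38%. Stable disease became PR in 1% to 8% of patients; the reverse happened in 0.6% or fewer.

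**The case against.** **Baseline selection is implied.** Section 11.0 measures against the baseline scan, and 11.221 asks for up to six of the largest dominant nodes. Both point to a list drawn up at baseline. That has force, but no lock is written. Even with a frozen list, 11.0 still removes the substitute, and the first example shows that this alone can change the category.

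**Entry of the shrunken lesion is only permitted.** A reader might infer that the swapped-out lesion must join the sum. No section says so, and where more than six lesions are eligible it may not be chosen. The supportable statement is that it may enter.

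**The bias is not always favorable.** A reader might infer that every swap helps. The substitute need only be ablatable and may itself be responding. PR also requires no growth in other nodes and no new sites (11.222, 11.226). Mainly upward is as far as one can go.

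**PET criteria may apply.** Section 11.1 bases response on PET/CT, while 11.227 calls for CT criteria for PR. The SPD arithmetic holds only on the CT reading. Under PET the swap still changes which lesions are scored, by another route.

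**Shrinkage in A is real.** A was never ablated, and 16.41 treats such lesions as the marker of systemic effect. That stands. The fault is not in counting A but in letting its shrinkage decide whether it counts.

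**Conclusion.** The concern holds in a limited form. Following the plan as written, early response to pembrolizumab can determine which lesions are scored for the primary endpoint, and the likely effect is to raise apparent ORR. Removal of the substitute follows directly from 11.0; entry of the planned lesion is left open.

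The size cannot be read from the documents, because neither the swap frequency nor the agreement between lesions is given. The rates of 10.3% and 19.1% assume one and two conversions and are not predictions. They show that a single conversion would about double the nominal 5% error. A reader might infer that the trial's ORR is inflated by a known amount; the documents do not support that. The change is worth making because the route leads straight to the primary endpoint and is cheap to close.

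**What to change.** In 11.0 and 16.41:
1. Record the index lesions, the planned cryoablation lesion and one named backup (where one exists) on the baseline scan before Cycle 1 Day 1. Admit no lesion to the index set afterwards.
2. Leave both the planned and the backup lesion out of baseline and follow-up response measurement in every patient, swapped or not, together with any lesion injected with DC without ablation.
3. Report the number of swaps, and a sensitivity analysis of ORR with swapped patients counted as non-responders.
4. Reconcile 11.1 with 11.227 on whether PET/CT or CT criteria define PR.

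The exclusion has to apply to everyone. Dropping the planned and ablated lesions only after a swap still conditions on early change; in the simulation above that left apparent ORR at 31% to 36%. The rule does not ensure that any given patient stays at stable disease: in the first example C alone would still be scored at -55%. What it does is settle that choice before treatment.

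The cost is wording and a baseline CRF field, with no extra scans and no change to which tumor is treated. The sum loses one lesion. Under 3.15 at least one remains when the swap goes to the named backup, but measurement is noisier in patients with few lesions. If some other lesion is ablated, 11.0 removes it as now, and the patient is flagged as swapped.
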